8.0 Data Collection and Management Procedures

Muscle activity data, as well as isometric strength data will be collected on a stand-alone desktop computer and stored electronically on that PC as well as a backup hard drive. Access to this data on the PC and the external hard drive will be protected via a password that only the PI and his students will have access to. Both the PC and external hard drive are located in our lab, which is locked.

Data collected using performance-based balance and mobility tests will be recorded on paper data collection forms. Collected data will be stored in subject-specific folders, located in a locked filing cabinet (separate from consent form cabinet). Keys for this cabinet will be kept in a lockbox with a 4-digit passcode that only the PI and his students will know.

Survey responses collected during experiments will be entered and stored in a secured REDCap database. REDCap will only be assessable to study personnel including the PI, Co-I, and other research staff via password protection. This ensures that de-identified data will be secure yet available to all investigators involved in the study.

A master code sheet linking subject names to study ID # will be kept in the PI's or site PI's offices in a locked cabinet. This location is separate from where the data is collected and stored. Only the PI or site PI will have access to this master list. The master list is necessary for the multiple visit portion of the study. When subjects return for their 2nd and 3rd visit we will have to assign them the same ID# as in previous visits.

9.0 Data Analysis

Data will initially be processed in the lab on the stand-alone PC and then backed up to the external hard drive. The PI and his students will perform additional analyses on computers in their office space that are password protected. Data analysis may include the use of such computer programs as Matlab, SPSS, and Excel.

At no point will any data on the lab stand-alone PC, the PI's computer, or those of his students contain any private health information or data that could be linked to specific subjects via personnel identifiers.

10.0 Quality Control and Quality Assurance

After every assessment, the PI and/or one of his students will review that all inclusion and exclusion criteria for screening were met. They will also review that all data was collected in a manner that is consistent with what is outlined in the protocol and consent form. Any departure from the protocol or failure to meet inclusion/exclusion criteria will be reported to the IRB and the data will be deleted.

Collected data will be regularly entered into entered into REDCap and reviewed by the site PIs. This will provide regular review of the data quality.

11.0 Data and Safety Monitoring

To ensure the safety of subjects and keep personal information private the following procedures will be followed. In the event of an injury or adverse event we will call 911 if necessary, and report any adverse event to the IRB in a timely manner (within 3 business days). Subjects requesting medical treatment will be directed to the appropriate source of treatment. These adverse events could be physical injury or a breach in confidentiality. We will maintain a safety log of adverse events (falls, skin irritation, breach of confidentiality etc) for each session that is kept in a locked drawer in the lab. A brief summary of the experiment, whether any adverse events occurred, when they were reported, and what actions will be taken to prevent them in the future will be recorded after. An example of this log is attached to this application ("Research Safety Log").

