1.0 Project Summary/Abstract

The **objective** of this research project is to evaluate hip muscle function among lower limb prosthesis users, its contribution to balance and mobility, and the effect of prosthetic socket design on amputated limb hip muscle strength and endurance. Traditional socket designs can provide pelvic support that interferes with hip motion. They may also reduce the effort required from amputated limb hip muscles to stabilize the hip and amputated limb, risking further loss of muscle mass and strength beyond that due to amputation. Long-standing use of sockets with pelvic support may therefore intensify amputated limb muscle loss and weakness, leading to challenges with walking and balance, increasing the effort required to walk, and contributing to degenerative changes in the hips and knees.

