Aim 2: Test whether socket design alters hip muscle function among lower limb prosthesis users. We hypothesize that walking with different socket designs will: i) require different residual limb hip muscle activity, as evidenced by greater peak muscle activity, as well as altered onset and offset times, and ii) result in short- and long-term gains in residual limb hip muscle strength and endurance, as evidenced by an increase in average peak torque, rate of torque development, and resistance to fatigue. To test these hypotheses electromyographic signals will be recorded from hip muscles on the residual limb of unilateral lower limb prosthesis users walking at a range of speeds. Hip muscle strength and endurance will be measured using a motor-driven dynamometer. Assessments will be made at baseline in established wearers of an ischial containment socket, and then again at eight and 42-weeks after being fit with a sub-ischial socket. Step count activity data will be collected to determine the extent to which gains in residual limb hip muscle strength and endurance are due to changes in hip muscle activation versus an increase in physical activity.

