7.0 Expected Risks/Benefits

Foreseeable, potential risks for prosthesis users and able-bodied controls participating in this study include: a) fatigue resulting from long periods of standing or walking, b) injury from mechanical failure of the equipment (e.g., treadmill, motorized dynamometer), c) falling during administration of the study protocol, d) electrical shock associated with recordings of

electromyograms (EMG), e) irritation to the skin from medical grade tape used to attach sensors to the body, or f) embarrassment. The risk associated with these events is expected to be low. We have attempted to reduce known potential risks. We do not know of alternative procedures that can reduce these risks and provide the same information. The safety precautions associated with the potential risks are as follows:

- a) Loss of balance and falls: All study personnel will undergo falls training led by the PI. This training will familiarize them with appropriate spotting techniques to catch a participant if they begin to fall.
- b) Fatigue: The test sessions may last up 3 hours, however, only 90 minutes are dedicated to study procedures. This duration may nonetheless be fatiguing to some participants. The majority of the time is devoted to participant preparation and instrumentation, a large part of which is done while the participant is either sitting or lying down. We will enforce sitting breaks of at least 5 minutes every 20 minutes of experimentation. The breaks will only end with the participant's consent and participants will be continually monitored during testing by the evaluator and trained assistants for fatigue and instability.
- c) Mechanical injury: The treadmill and motorized dynamometer are physically limited by the motor torque and cannot deliver excessively large, injury-causing perturbations. They are equipped with limit switches that shut down power if they reach near the end range of their capabilities. Software limits further limit uncontrollable movements of the treadmill and dynamometer. There is an emergency stop button next to the experimenter and on the treadmill as well as the dynamometer for participants. Additionally, all equipment will be inspected for safety as part of the set up routine for each data collection session.

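### Harms from wearing the study socket between Aim 2 visits are not systematically collected as adverse events, so an empty safety log would not show that the socket caused no harm

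*Combined protocol and SAP*

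**What the plan says.** All references are to the combined protocol and SAP.

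- **Safety log (Section 11.0).** "We will maintain a safety log of adverse events (falls, skin irritation, breach of confidentiality etc) for each session". Each entry is to hold "A brief summary of the experiment, whether any adverse events occurred, when they were reported" and the actions taken to prevent recurrence. Staff must also "report any adverse event to the IRB in a timely manner (within 3 business days"; this duty is not worded as limited to sessions.
- **Risk list (Section 7.0).** The list opens "Foreseeable, potential risks for prosthesis users and able-bodied controls participating in this study include" and begins "a) fatigue resulting from long periods of standing or walking, b) injury from mechanical failure of the equipment (e.g., treadmill, motorized dynamometer". It goes on to falls during testing, electrical shock from EMG recording, "irritation to the skin from medical grade tape used to attach sensors to the body", and embarrassment, which is later extended to loss of confidentiality. The socket does not appear.
- **Intervention (Section 3.0, Aim 2).** Established users of an ischial containment socket are assessed at baseline and again "eight and 42-weeks after being fit with a sub-ischial socket". Section 2.0 presents use at home, in the community and at work as the attraction of the approach. Section 6.0 has step activity monitored for two weeks before each follow-up test.
- **Rationale (Section 1.0).** Traditional sockets may "reduce the effort required from amputated limb hip muscles to stabilize the hip and amputated limb".
- **Measures at each visit (Section 6.0).** These include health information, a falls question about the past year, PROMIS 29 (general health), the Socket Comfort Score and balance confidence.
- **Analysis (Section 12.0).** Aim 2 is a descriptive pilot in at most 10 people. It covers changes in muscle activity and strength and names no harm outcome.

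**The concern.** The intervention acts mainly outside the laboratory, while the safety procedures are written around the laboratory visit. The only skin risk named is from tape, and the only falls risk named is during testing. A person fitted with a different type of socket could have a skin problem, residual-limb pain or an injury months before the next visit, and nothing in the plan prompts anyone to ask about it.

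What is at stake is how the pilot is read. If Aim 2 reports gains in strength beside an empty log, a reader may take the log as evidence that the socket was well tolerated, and a larger study may be planned on that basis. A log that depends on participants volunteering events cannot carry that inference.

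**Working it through.** The plan states no figure on this point, so there is none to reproduce. The check is whether any channel in the plan would record a socket-related event that occurs at home and has resolved by the next visit.

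**1. Length of the gap.** Follow-up visits are at weeks 8 and 42 (Section 3.0), so the longest interval is 42 − 8 = 34 weeks. No contact for reporting or asking about events in between is described.

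**2. The channels side by side.**

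| Channel | Reaches home wear? | What it lacks |
|---|---|---|
| Safety log (11.0) | Only if an event is disclosed and the phrase on sessions is read broadly | No question that prompts disclosure |
| IRB duty (11.0) | Yes, for events staff learn of | No means of learning of them |
| Falls question (6.0) | Yes, for falls | Asks for no date and no socket worn; recall includes pre-socket time |
| Socket Comfort Score (6.0) | As a score taken at the visit | Not an adverse-event record |
| PROMIS 29, health information (6.0) | Possibly | Described as characterising participants; no since-last-visit event question stated |
| Aim 2 analysis (12.0) | No | No harm outcome named |

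No row gives a dated, prompted record of skin, residual-limb, pain or injury events since fitting.

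**3. How far the falls question helps.** With a 52-week recall and a visit w weeks after fitting, the share of the recall window that precedes the socket is (52 − w)/52.

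- Week 8: (52 − 8)/52 = 44/52 = 85%.
- Week 42: (52 − 42)/52 = 10/52 = 19%.

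The week 42 question therefore covers all the time in the new socket but mixes in 10 earlier weeks. The week 8 question is mostly about the old socket. Section 6.0 counts the weeks from baseline testing, whereas Section 3.0 counts from fitting. If fitting follows baseline by f weeks and the baseline clock applies, the share becomes (52 − w + f)/52, so 85% and 19% are then minimum values.

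**4. What complete collection could show with n = 10.** The chance of at least one affected participant is 1 − (1 − p)^10. The 42-week risks p below are assumptions, since the documents give none.

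| Assumed p | Chance of at least 1 of 10 |
|---|---|
| 5% | 40% |
| 10% | 65% |
| 20% | 89% |
| 30% | 97% |

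Even with complete collection, 0 of 10 leaves an upper 95% limit of 1 − 0.05^(1/10) = 25.9% (one-sided) or 1 − 0.025^(1/10) = 30.8% (two-sided exact). Those limits hold only if everyone was asked about the whole period. Without that, an empty log does not support even these wide bounds.

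**The case against.** The strongest reply is that the plan captures more than the log sentence suggests.

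- The IRB duty covers any adverse event, so an event at week 20 that staff hear about by telephone or at week 42 is reportable.
- The phrase about sessions can mean one entry per session, with room for anything disclosed there, rather than a log confined to events during testing.
- Falls, general health, socket comfort and balance confidence are asked again at both follow-up visits. The week 42 falls question spans the whole 34-week gap.
- The example safety log is not in the text and may carry prompts.
- Aim 2 is a descriptive pilot on muscle function, and no section plans a claim of no harm.

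Most of this stands, and it rules out a stronger reading. A reader might infer that home-wear harms are missed altogether, never logged and never reported. The documents do not support that: the reporting duty is general, the log wording is ambiguous, and partial measures exist. A reader might also be tempted to express the gap as session hours over wear hours, or to contrast an empty log with a supposed true event count. Both would need a wear schedule or an event rate that the documents do not give, and both presuppose the narrow reading of the log. Nor do the documents show that greater demand on the hip is itself a harm; Section 2.0 treats the added work as the hoped-for benefit.

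What the reply does not supply is a prompt. A duty to report does not help staff learn of events, and none of the repeated measures is set up as an adverse-event record.

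**Conclusion.** The concern holds as a gap in systematic collection. Harms from wearing the study socket between visits are not actively sought, the socket is absent from the listed risks, and an event that resolves and is not volunteered can go unrecorded. An empty Aim 2 log could not be read as evidence that the socket caused no harm. The number of events lost cannot be estimated; the sizes that can be stated are the 34-week interval and the 85% and 19% pre-socket shares of the falls recall, counted from fitting.

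This rests on two assumptions: that the socket is worn in daily life, which the rationale and step monitoring imply although no wear schedule is stated, and that the example log adds no since-last-visit questions. The consent form was not available, so nothing is concluded about what it says. No planned estimate of muscle function is affected. The change should be made because the gap concerns the safety of the intervention under study and is cheap to close.

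**What to change.** 1. **Section 11.0.** State that for Aim 2 the log covers the whole period from socket fitting to the week 42 visit, wherever an event occurs.
2. **Weeks 8 and 42, before testing.** Ask a fixed set of questions on falls, skin, residual-limb, pain and injury events since fitting (week 8) or since the last visit (week 42). Record onset date, socket worn at the time, and outcome. Keep the past-year falls question as a characterisation measure.
3. **Between visits.** Give participants a study contact for reporting events. The plan does not say how the activity monitor is issued, so this fix does not rely on that as a contact.
4. **Section 7.0.** Add wearing the study socket to the risks.
5. **Section 12.0.** Tabulate these events descriptively for all fitted participants alongside the Aim 2 results, and note what 0 of 10 can and cannot exclude.
6. **Sections 3.0 and 6.0.** Reconcile whether the weeks count from fitting or from baseline testing, so that the period at risk is defined.

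The cost is protocol wording and a few minutes at two existing visits for at most 10 people. The downsides are reliance on recall over up to 34 weeks, which the study contact only partly offsets, and a larger number of reported events.

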12.0 Statistical Considerations

Descriptive statistics: Measures of central tendency and variation will be used to describe participant characteristics, and all study variables (e.g., balance and mobility tests, muscle strength). Normality, homogeneity of variance, and multicollinearity will be evaluated using the Shapiro-Wilk test, Levene's test, and, Pearson's r (r<.90) respectively. If assumptions are met data will be analyzed with parametric tests, otherwise non-parametric tests will be used. Statistical analyses will be performed using SPSS 25 (Chicago, IL).

Aim 1: A 2-way mixed-MANCOVA (multiple analysis of covariance), or non-parametric equivalent, will be used to test for statistically significant differences in strength and endurance between legs (prosthetic, intact, and control) as well as across muscle groups while controlling for potential covariates (e.g., residual limb length, etiology). Multiple linear regression will be used to determine how much variation (i.e., difference) in balance and mobility outcomes (e.g., Four Square Step Test; physical activity) among transfemoral prosthesis users can be explained by differences in hip muscle strength and endurance.

Aim 2: As a pilot study, descriptive analyses including measures of central tendency (mean) and dispersion (95% confidence intervals), along with effect sizes (e.g., Cohen's d, common

language effect size), will be used to evaluate changes in residual limb hip muscle activity, strength, between test sessions while controlling for covariates. Correlation analyses will be used to determine if any observed changes in hip muscle strength can be attributed to changes in hip muscle activity (i.e., EMG) or physical activity (i.e., step count).

Power Analysis: Choosing a power of 0.80 and a type I error rate (α) of 0.05, pilot data from lower prosthesis users (n=2) and able-bodied persons (n=2) estimate that a sample of 20 people per group will be sufficient to identify differences (p<0.05) in hip muscle strength and endurance between the residual limb, intact limb, and able-bodied persons using a mixed analysis of variance (ANOVA) (Aim 1). As a pilot study, enrollment in Aim 2 will be limited to 10 unilateral lower limb prosthesis users.

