13.0 Regulatory Requirements

13.1 Informed Consent

When participants arrive in the lab, they will meet study staff and review the informed consent form with him and/or other research personnel. The PI and/or other research personnel will review all of the key points in each section and allow the participant to read the consent form and ask any questions. Participants will participate in the experiment only after granting full informed consent. Consent capacity will be assessed by a discussion of the proposed research project. During the consent process, a series of questions can be asked to assess understanding of key issues. Such questions will relate to the purpose of the research and the foreseeable risks and anticipated benefits of study participation or understanding of the voluntary nature of research and the elements of consent, including the right to be informed about appropriate alternative procedures or courses of treatment that may be available.

All participants will be told that if they choose not to consent, at this time or anytime during the study, they will be allowed to stop and leave. They will also be told that by consenting at the start of the study they are not required to finish the study. They are free to end their participation at any time without having to give an explanation. They can then decide whether they want their data deleted or if it can still be included in our analyses. This will be documented in a revocation form. Participants will also be told that will still be compensated for their time spent in the study prior to terminating their participation.

During the consent process all participants will be given the opportunity to consent to having video taken during their experiment. They will be asked to check yes or no and initial beside their selection. Options for the use of the video will include reviewing the video to make sure all protocols were performed appropriately, as well as use in presentations at conferences. Participants will be told that their selection to consent to video will not affect their eligibility to participate in the current study.

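### The Aim 1 MANCOVA in SPSS keeps only complete rows, so one unfinished muscle test discards other valid data, and the plan has no missing-data rule and no allowance above 20 per group

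*Combined protocol and SAP*

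**What the plan says.** Section 12.0 (Aim 1) tests strength and endurance with one model: "A 2-way mixed-MANCOVA (multiple analysis of covariance), or non-parametric equivalent, will be used". Its factors are compared "between legs (prosthetic, intact, and control) as well as across muscle groups", with adjustment for covariates; residual limb length and etiology are the examples. The software line reads "Statistical analyses will be performed using SPSS 25 (Chicago, IL"; the procedure is not named.

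The power paragraph of the same section starts from "Choosing a power of 0.80 and a type I error rate (α) of 0.05". It cites "pilot data from lower prosthesis users (n=2) and able-bodied persons (n=2") to "estimate that a sample of 20 people per group will be sufficient to identify differences (p<0.05) in hip muscle strength and endurance", "using a mixed analysis of variance (ANOVA) (Aim 1"). It does not say whether 20 means enrolled or analysed.

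Section 6.0 (Hip Muscle Strength and Endurance) measures four hip muscle groups, with fifteen consecutive maximal efforts in each test position. Peak torque and rate of torque development use the first three repetitions. The fatigue index compares the first five with the last five. Two body positions are named, each serving an opposing pair of muscle groups.

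Gaps are foreseen elsewhere. Section 7.0 lists fatigue as a risk. Section 13.1 tells participants that "they will be allowed to stop and leave" if they no longer consent. Section 10.0 deletes data after a protocol departure. No section gives a missing-data rule, an analysis set or an allowance for incomplete tests.

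**The concern.** The multivariate and repeated-measures GLM procedures in SPSS, where a mixed MANCOVA is run, use a row only if every dependent variable and covariate in the model is present. This is a standard property of the procedure; the documents do not mention it.

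The strength and endurance measures need different amounts of data. A user who stops a set at repetition ten has valid peak torque and rate of torque development but no fatigue index. In a joint model that gap removes the whole row: the other muscle groups of that limb or, if both limbs share a row, everything the participant contributed.

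Covariates work the same way. Residual limb length and etiology of amputation have no value for able-bodied controls; entered as blanks, they would remove every control. Surgical technique, which Section 6.0 seeks through a survey sent to the surgeon, is not a listed covariate, but the list is open. If entered, it would remove each user whose surgeon does not reply.

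At stake are the size of the sample behind the study's main inferential test, and whether that sample still represents those enrolled.

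**Working it through.** **The plan's own figure.** The 20 per group cannot be reproduced, because no effect size, SD, within-person correlation or sidedness is given. It can only be solved backwards. With two groups of 20, two-sided α = 0.05 and power 0.80:

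- normal approximation: d = (1.960 + 0.842) × √(2/20) = 0.886
- noncentral t: d = 0.909
- paired comparison of residual and intact limb, 20 users, noncentral t: d = 0.660

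**Tests per row (k).** The documents allow several layouts.

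- k = 8: four muscle groups × two limbs, with both limbs of a user in one row.
- k = 4: one limb per row with four muscle groups; or both limbs in one row with two positions per limb counted as the tests.
- k = 2: one limb per row with two positions as the tests.

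The number of control limbs tested is not stated, so eight is derived for prosthesis users only.

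**Complete rows.** The missing rate p per test is an assumption: 2%, 5% or 10%. If tests go missing independently, the share of complete rows is (1 − p)^k. If the same people miss every test (full overlap), it is 1 − p.

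- k = 8: 0.98^8 = 0.851; 0.95^8 = 0.663; 0.90^8 = 0.430
- k = 4: 0.98^4 = 0.922; 0.95^4 = 0.815; 0.90^4 = 0.656
- k = 2: 0.98^2 = 0.960; 0.95^2 = 0.903; 0.90^2 = 0.810

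Multiplied by 20, with the power of a two-group t test at d = 0.909 and both groups reduced alike (noncentrality d√(n/2), 2n − 2 degrees of freedom) in brackets:

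| Layout | p = 2% | p = 5% | p = 10% |
|---|---|---|---|
| k = 8, independent | 17.0 (0.73) | 13.3 (0.61) | 8.6 (0.42) |
| k = 4, independent | 18.4 (0.77) | 16.3 (0.71) | 13.1 (0.61) |
| k = 2, independent | 19.2 (0.78) | 18.1 (0.76) | 16.2 (0.71) |
| Full overlap | 19.6 (0.79) | 19.0 (0.78) | 18.0 (0.75) |

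**Enrolment needed to keep 20 complete rows**, as 20 / (1 − p)^k rounded up: 24, 31 or 47 for k = 8, and 22, 25 or 31 for k = 4. An analysis that keeps partial records would not need this full inflation.

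**The case against.** A reader might infer that any missing test drops the participant from the whole analysis. The documents do not show this. Leg has three levels, and control legs belong to other people, so leg cannot be wholly within-person. A two-way mixed layout may well put each limb in its own row, with muscle group as the repeated factor; a gap then costs one limb's row. That layout treats two limbs of one person as independent, which is a separate weakness. Eight separate sets is also an inference, since Section 6.0 ties the fifteen efforts to test positions and names two. The non-parametric route is unspecified, so its handling of gaps cannot be determined.

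A reader might also infer that the sample will fall well below 20. That rests on an assumed rate and on independence. If gaps concentrate in people with weak or painful limbs, fewer people are lost: 19 of 20 remain at 5% with full overlap. Aim 1 is a single session with enforced rests, so nothing is lost between visits. Separate strength and endurance runs would protect the strength data. A participant who withdraws and asks for deletion is lost under any method.

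These points limit the size of the loss. They do not remove the mechanism: under every layout above, an unfinished set discards valid values that another model in the same software would keep, and nothing in the plan allows for it.

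**Conclusion.** The point holds as a weakness of method, of unknown size. Under the assumed rates of 2% to 10%, complete cases range from 19.6 down to 8.6 of 20, depending on layout and overlap.

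Two stronger conclusions are not supported. One is that power falls below 0.80 by a definite amount. The 0.80 rests on two pilot participants per group and on a mixed ANOVA rather than the planned MANCOVA, and it cannot be reproduced, so the bracketed powers are illustrations. The other is that the residual-limb deficit is biased toward zero. That is plausible if weak or painful limbs stop early, but nothing in the documents shows it.

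The conclusion rests on the standard complete-row behaviour of SPSS GLM and on strength and endurance being analysed jointly, as Section 12.0 indicates. The blank-covariate problem for controls needs no assumed missing rate, only that the covariate is entered as missing. The change is worth making because it costs little and holds under either layout.

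**What to change.** In Section 12.0, replace the MANCOVA with one linear mixed model per outcome (SPSS MIXED). Use participant as a random effect, and leg, muscle group and their interaction as fixed effects. This keeps every available limb-muscle value and accounts for two limbs coming from one person. State how many control limbs are tested.

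Report the number of missing or unfinished tests by limb, with the reason.

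Do not enter a covariate that is blank for a material share of participants in a model that deletes incomplete rows. This covers surgical technique if surveys are not returned, and residual limb length and etiology when controls are in the model. SPSS MIXED also drops rows with a blank covariate, so the rule is needed after the change as well.

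The cost is a change of wording, with the same software and data. There are two limits. Several tests replace one multivariate test, so a primary outcome must be named or a multiplicity rule stated. And the mixed model reduces bias only if missingness is explained by observed data; if sets are missing because of strength that was never recorded, bias can remain, which is why the report of reasons matters.
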